3.2 Outcomes

The primary outcome measure is height gain in cm during the pubertal induction period, since this can be accurately determined in the context of an international framework. Secondary outcome measures include final adult height, systolic blood pressure, aortic root diameter, uterine size and shape, bone mineral density, adherence and dropout rate.

Table 1 Outcome measures to be analysed at the end of pubertal induction in girls with Turner syndrome using either an oral (see Tables 2a and 2b) or transdermal (see Tables 3a and 3b) 17- β estradiol regimen approved by the Turner Syndrome Working Group of ESPE.

Induction period is normally 3 years (plus 6 months for very short girls), exceptionally 2 years for girls presenting late (e.g. >14 years), minimum follow up is during induction period but where possible, follow up is to final adult height.

Primary outcome measure

Pubertal height gain, i.e. increase in height in centimetres during the (usually) 3-year pubertal induction period

Secondary outcome measures

- Final adult height in centimetres & population-specific SDS
- Change in population-specific height SDS between start and end of pubertal induction
- Breast development (clinical assessment)
 - Tanner B4-5 reached
 - Satisfactory breast shape (ie not tubular, no overdevelopment of areolae) according to attending clinician (graded as satisfactory or unsatisfactory)
- Cardiovascular health
 - Systolic & diastolic blood pressure at the end of induction (lowest of three readings or mean values if recorded by ambulatory 24-hour blood pressure monitoring
 - Change in aortic root diameter and aortic size index between start and completion of induction
- Patient satisfaction; adherence/compliance with treatment
 - Percentage drop-outs from either regimen
 - Average of good, reasonable and poor rating with adherence during pubertal induction (3 years ± X months)
 - Patient satisfaction with shape and size of breast (scoring 1-5 where 5=best)
 - Patient satisfaction with mode of administration (scoring 1-5 where 5=best)
- Uterine health and sex hormone profile at the end of induction
 - Uterine length and volume, endometrial thickness
 - Uterine shape and fundo-cervical ratio
 - LH and FSH
 - Serum 17-β estradiol

- Skeletal age and bone health
 - Change in bone age/chronological age per year
 - Change in size-adjusted whole body lumbar spine and hip bone mineral areal density (BMAD) (z-score) before and after induction
- Metabolic profile

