4.3 Oral progesterone administration

An oral progestogen such as Dydrogesterone (9β ,10 α -pregna-4,6-diene-3,20-dione) 10 mg; micronised progesterone 100 mg; and medroxyprogesterone acetate 5 mg initially [13] is recommended but depends on local availability. A duration of 10 days each calendar month is recommended, in keeping with the Cincinnati guidelines [13].

To allow maximum time for uterine and breast development with unopposed estrogen, pubertal staging and where possible pelvic ultrasound examination should be carried out at the time of first breakthrough bleeding-so that endometrial thickness and uterine size can be determined [21].

Depending on the assessment, a decision should be taken to either introduce progesterone, or delay doing so and review after 6 months (or earlier if breakthrough bleeding becomes problematic).

Features suggesting postponing progesterone treatment include: Tanner stage B3 breast development or less: uterine length < 5 cm, i.e. the 50th centile for general Scottish population aged 13 years [26], fundo-cervical ratio \leq 1 (i.e. infantile or cylindrical configuration) and endometrial thickness \leq 2 mm. Features suggesting that progesterone should be introduced include Tanner B4-5 development, uterine length \geq 5 cm, fundo-cervical ratio > 1 (pubertal or pear-shaped configuration) and endometrial thickness > 2 mm.

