4.5 Data collection before and during pubertal induction

Table 4 shows the recommended information to be collected before, during and at the end of pubertal induction, and until adult height, i.e. height velocity < 2 cm/year.

TABLE 4 Recommended measurements before, during and at the end of pubertal induction with either transdermal or oral 17-β
estradiol grouped according to priority – essential and desirable.

Variable	Before induction (± 6 months)		End of Years 1 & 2	End of Year 3	Comment	
ESSENTIAL	(2 o montho)	visito				
Karyotype	X				From time of diagnosis	
Auxology Height (cm)	x	x	x	х		
Weight (kg)	X	Х	X	Х	 Previous growth data will be requested, to enable calculation of a) height velocity, using 12 (±1) month interval, during previous year; and GH responsiveness – derived from height/weight status one year prior to, at the start of, and one year after starting GH. 	
Height velocity (cm/yr)	X		X	Х		
Measured parental heights (where available)	X					
Breast and pubic hair stage (1-5)	X	Х	X	Х		
Systolic & diastolic blood pressure (mm Hg)	Х	Х	Х	Х	Lowest of three consecutive readings using Dinamap V100 or similar device	
Adherence to treatment		X	Х	Х	Scored according to estrogen doses missed per month as good (≤ 2) moderate (≤ 4) and poor (> 4)	
Adverse events/illness		Х	Х	Х	All adverse events (e.g. injury, intercurrent infection) irrespective of relevance to growth and puberty	
FSH, LH	X			Х		
Free T4 and TSH	Х			Х		
Liver function	Х		Х	Х		
HbA1c	Х			Х		
Concurrent treatment	Х	Х	Х	Х	GH, L-T4, Oxandrolone	
DESIRABLE	1					
Final adult height					Measurement once height velocity < 2cm/year	
Bone age	Х		Х	Х	Assessed using 'BoneXpert', where available	
Sitting height	X	X	Х	Х		
Echocardiography	X			Х	Including measurement of aortic size index	
Pelvic ultrasound	Х		X	Х	Uterine length, shape and volume, endometrial thickness	
DXA BMC	Х			Х	Hip and lumbar spine z-score Total body BMD	
Fasting lipid profile	Х			Х	Cholesterol, triglycerides, low and high-density lipoproteins	
Coagulation studies	X			Х		
Serum estradiol	X			Х	Beginning of Year 4 (see Table 2)	
Serum IGF-I	X		Х	Х	Keep +1.5 -2.5 SD of reference range	
24h continuous ambulatory blood pressure	X			Х		
Fasting blood glucose and insulin	Х			Х		

Abbreviations

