FSH = follicle stimulating hormone; LH = luteinising hormone; fT4 = free thyroxine; TSH = thyroid stimulating hormone; DXA = dual X-ray absorptiometry; BMC = bone mineral content; BMD = bone mineral density; GH = growth hormone; L-T4 = levo-thyroxine. *4-monthly visits are recommended; however 3-6 monthly may be more suitable for some participating centres.

It should be noted that measurements such as height, weight, pubertal stage and blood pressure are marked as 'essential' and are within the scope of any paediatric service caring for girls with TS. By contrast, 'desirable' measures should be undertaken at the clinician's discretion, and take account of the resources available in the participating centre.

Since height gain during induction is the agreed primary outcome measure, previous height and weight data from one year before, at the time of and one year after the start of GH treatment and at least yearly thereafter, together with GH dose and possible oxandrolone treatment, are required to assess GH responsiveness [29,30].

Karyotype (normally available from time of diagnosis) is essential information.

At each visit, measurement of height, weight, blood pressure, pubertal stage, adherence (scored according to the number of estrogen doses estimated by the family to have been missed per month), recording of adverse events, and concurrent treatment are required.

Note that the family will be asked at each visit about **any** adverse events including minor injury, intercurrent infection, middle ear problems and gastrointestinal symptoms, and summarised at the end of each year by the clinician.

Annual biochemistry for thyroid function and liver function, FSH, LH and estradiol levels will be carried out as part of normal clinical practice.

Echocardiogram to define the anatomy of the heart and great vessels, with measurement of aortic root diameter at the annulus, and aortic size index (aortic root diameter divided by body surface area), is recommended before and at the end of induction.

Pelvic ultrasound, measuring uterine length, fundo-cervical ratio, uterine shape (infantile, cylindrical and pubertal) and endometrial thickness are also recommended before and after induction.

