6.2 Sample size

Mean (SD) height gain during three years of pubertal induction in the UK clinical trial of Gault et al [26] in which TS girls were treated with a consistent dose of GH has been calculated as 12.2 (3.5) cm. A mean difference of 2.5 cm between transdermal and oral regimens is considered clinically significant, giving a fractional effect size (f) of 2.5/3.5 = 0.71. Using the Lehr formula where $n=21/f^2$ gives the number of patients in each arm of the study required for 90% power at the 5% level [31], the number would be 42. However, given the covariates including age at diagnosis, karyotype, age at starting growth hormone therapy, differing dosage regimens, and use or not of Oxandrolone amongst the enrolled patients, a recruitment target of twice the power calculation, i.e. up to 84 in each treatment arm, is considered desirable so as to adjust for potential confounding factors. Note that this target of 84 in each treatment arm applies to girls undergoing the full 3-year induction period and does not include girls undergoing the shortened induction period.

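### Breast stage is recorded on the full 1–5 scale, but the outcome table compares it only as B4-5 reached or not, so a B4 versus B5 difference cannot show

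*Protocol*

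**What the plan says.** Table 1 in section 3.2 lists the outcomes to be analysed at the end of induction. Under breast development it gives two items, both yes/no: "Tanner B4-5 reached", and the clinician's view of breast shape, "graded as satisfactory or unsatisfactory". A separate item in the same table is "Patient satisfaction with shape and size of breast (scoring 1-5 where 5=best".

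Table 4 in section 4.5 lists "Breast and pubic hair stage (1-5") among the essential measurements: before induction, at visits, at the end of Years 1 and 2, and at the end of Year 3. The text below the table repeats this: "At each visit, measurement of height, weight, blood pressure, pubertal stage" and other items are required.

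Section 4.3 uses the same grouping for a clinical decision during treatment: "Features suggesting that progesterone should be introduced include Tanner B4-5 development". B3 or less is listed there among the features on the other side.

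Section 4.6 plans multivariable regression with a confounder set established for each outcome. It names no model for breast stage. Section 6.2 sizes the study on height gain only. No expected B4-5 rate, target difference or power is given for breast stage.

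**The concern.** Every centre must record a five-level ordinal measurement, and the outcome table then reduces it to two levels. Girls at B4 and B5 count as equal, and so do girls at B1, B2 and B3. If one regimen brings more girls from B4 to B5 by the end of induction, the listed stage outcome shows nothing. The absence of a difference on it could then be taken as equal breast development.

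A cut also usually costs power when the effect is a general shift along the scale, and the cost rises as the share above the cut approaches 100%. The choice sits in Table 1, which defines the endpoint, so an analysis plan that follows the protocol inherits it.

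**Working it through.** **The plan's own figure.** Section 6.2 takes a three-year height gain that "has been calculated as 12.2 (3.5) cm" and states: "A mean difference of 2.5 cm between transdermal and oral regimens is considered clinically significant". With f = 2.5/3.5 = 0.71, Lehr's formula gives 21/0.71² = 41.7, so 42 per arm, doubled to 84. This reproduces. It concerns height gain only; the breast calculations below borrow just the 84 per arm.

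**Assumptions.** The protocol gives no stage distribution, so every distribution here is assumed. Other assumptions are 84 evaluable girls per arm, two-sided 5%, nobody left at B1, no confounder adjustment or matching, and (except in the last two checks) a common odds ratio of 2 at every stage boundary.

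**Formulas**, with n = 84 per arm:

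- Cut: power = Φ{[|p₂ − p₁| − 1.96·√(2p̄(1 − p̄)/n)] / √([p₁(1 − p₁) + p₂(1 − p₂)]/n)}.
- Ordinal: Wilcoxon test with ties, which is the proportional-odds score test. θ is the probability that a comparator girl is at a higher stage than a reference girl, plus half the probability of a tie. Power = Φ{(|θ − ½| − 1.96·√V₀)/√V₁}, where V₀ = (2/n)(1 − Σp̄ⱼ³)/12 and V₁ is the variance of the estimated θ under the alternative.

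**Worked case.** Reference B2/B3/B4/B5 = 5/15/50/30%. An odds ratio of 2 gives 2.6/8.5/42.7/46.2%, so B4-5 goes from 80.0% to 88.9%.

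- Cut: (0.0889 − 1.96 × 0.0559)/0.0555 = −0.37, power 35%.
- Ordinal: θ = 0.5959; (0.0959 − 1.96 × 0.0409)/0.0399 = 0.39, power 65%.
- Gain: 30 points.

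**Range at odds ratio 2:**

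| Reference arm at B4-5 | Reference arm at B5 | Power, cut | Power, ordinal | Gain (points) |
|---|---|---|---|---|
| 50% | 5% / 10% / 15% | 59% | 64 / 67 / 68% | 5 / 7 / 9 |
| 60% | 5% / 10% / 15% | 55% | 61 / 64 / 67% | 6 / 9 / 12 |
| 70% | 5% / 25% | 47% | 54 / 67% | 8 / 20 |
| 80% | 5% / 10% / 30% | 35% | 46 / 53 / 65% | 10 / 18 / 30 |
| 90% | 5% / 10% / 15% / 35% | 21% | 34 / 44 / 52 / 63% | 13 / 23 / 31 / 42 |

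Simulation agrees within about two points. At 90% it runs one to two points higher, hence about 24 to 43 points there when at least 10% are at B5.

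**Other effect sizes.** With 90/80/70/60/50% of the reference arm at B4-5 and B5 at 35/30/25/15/10%, the simulated gain is about 57/37/20/11/6 points at an odds ratio of 2.5. At an odds ratio of 1.5 it is about 16/12/8/6/1 points.

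**Difference only between B4 and B5.** With 80% at B4-5 in both arms and B5 at 24% versus 44%, ordinal power is 49%. With 90% at B4-5 and B5 at 27% versus 49.5%, it is 72%. The cut has about 5% in both cases, its false-positive rate.

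**Difference only between B3 and B4.** With B2/B3/B4/B5 of 5/25/45/25% versus 5/10/60/25%, B4-5 goes from 70% to 85%. The cut has about 65% power and the ordinal test about 25%. Here the cut is better.

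**The case against.** The strongest reply is that the cut has a meaning within the protocol. Section 4.3 separates B3 or less from B4-5 when progestogen is considered, so a target-reached outcome at that point is not arbitrary. The study is open and staging is a local clinical assessment, which is a reason not to lean on the B4/B5 boundary alone. This stands, and it is why the B4-5 percentage should stay as a reported result. It does not make the cut the best sole comparison of two regimens.

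A reader might infer that much of the power for this outcome is lost. The protocol does not show that: the gain runs from about 1 to 57 points depending on assumed inputs, and it is negative when the difference lies only at the B3/B4 boundary. A reader might also infer that nearly all girls are above the cut because induction is meant to complete puberty. The protocol gives no rate, and both regimens go on to a higher suggested dose after induction (oral from 15 to 20 microgram/kg/day in Table 2a), so B5 may still be uncommon at that time.

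It is also true that shape and patient satisfaction are compared. Shape is another yes/no item about form, and satisfaction is the girl's opinion; neither measures stage, though both make it less likely that the stage result alone would be read as the whole of breast development.

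Finally, an analysis plan that is not shown could add an ordinal analysis. It could, but it would then analyse something other than the endpoint that Table 1 names.

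**Conclusion.** The point holds in a limited form. It needs no assumption to say that the stage outcome, as Table 1 defines it, cannot show a B4 versus B5 difference although the data for it are mandatory.

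The size of the power loss is conditional. At 84 per arm and a common odds ratio of 2 it is about 5–12 points with 50–60% of the reference arm at B4-5, about 10–30 points at 80%, and about 24–43 points at 90%. The lower ends belong to distributions with few girls at B5; with only 5% at B5 and 90% at B4-5 the loss is about 13 points. These figures also ignore the matching and adjustment planned in section 4.6.

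The reading that the study is underpowered for breast development is not supported either, since no power is claimed for it. Breast development is one of many secondary outcomes and does not appear in the research question in section 3. This is a minor improvement; height gain and the target of 84 per arm are untouched.

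**What to change.** In Table 1, replace the yes/no item with breast stage (1–5) at the end of induction. Compare it between regimens with an ordinal (proportional-odds) model, using the confounder set established for this outcome under section 4.6 plus baseline breast stage. Keep the percentage reaching B4-5 in each regimen, with the between-regimen difference and its confidence interval, as a reported clinical summary.

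The cost is one line in Table 1 and one model, with no new data, visits or patients. The downside is that a common odds ratio is less familiar than a percentage and assumes a similar shift across stages. The retained B4-5 difference covers the case in which the regimens differ mainly at the B3/B4 boundary.

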4.2.1 Oral induction

The agreed oral three-year induction protocol, derived from the Dutch regimen of Bannink et al [23], together with a final (fourth) year, of maintenance treatment is shown in Table 2a. A 2-year protocol for older girls (e.g. aged >14 years) in whom a shorter induction period is desired by the clinician and family, is given in Table 2b

Dose is based on body weight and is recalculated at the beginning of each year.

 $17-\beta$ estradiol will be given in its micronized (e.g. Estrace) or hemihyrate (e.g. Cetura) form using 0.5 mg tablets which can be halved by the family.

Alternatives such as esters - $17-\beta$ estradiol valerate (e.g. Climaval and Zumenon) and hemihyrate preparations (e.g. Elleste solo and Estrofem) are acceptable but only available as 1 mg tablets so that participating centres would therefore need their pharmacy to prepare a suitable dose from a 1 mg tablet.

Girls receiving <0.25 mg daily with any preparation would also need their medication prepared by the pharmacist. Girls receiving <0.25 mg daily with any preparation will require their pharmacy to prepare the correct dose in capsule form, as currently practiced in The Netherlands using Cetura. (Documentation from Amalia Children's Hospital, Radboud University Medical Center, Nijmegen, available on request). In patients requiring ≥0.25 mg daily the dose will be rounded to the nearest 0.25 mg. Evening administration is recommended, to mirror the transdermal regimen.

Table 2a Three-year oral 17β -estradiol regimen for pubertal induction and, in italics, a suggested first post-induction year [21]. The dose is calculated according to body weight at the beginning of each year and given before sleep each night.

Year (months)	Dose of estradiol [microgram/kg/day]
1 (0-12)	5
2 (13-24)*	7.5
3 (25-30)	10
3 (31-36)	15
4 (37-48)**	20†

*Girls in whom low final height is anticipated or who are markedly short at the start of induction (defined as ≤3 standard deviations below the population mean) may be offered a slower induction by receiving an extra 6 months of 7.5 microgram/kg/day between Year 2 and Year 3. **Morning serum estradiol sample is recommended at the beginning of Year 4.

[†]This post-induction dose equates to about 1 mg daily. However, the dose required will vary between 1 and 4 mg daily, depending on patient sensitivity, most patients requiring at least 2 mg daily.

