4.2.2 Transdermal induction

Table 3 shows the agreed regimen, adapted from the Swedish protocol of Ankarberg-Lindgren [16] in which an overnight patch is applied for 10-12 hours during the first two years of induction. Dosage is weight-based and increased in accordance with weight at the clinic visit. Patches are applied on a healthy part of the skin (buttocks, belly or lower part of back), cutting the appropriate dose as described [21]. A new patch is applied on a different part of the skin. During the third year of induction the dose is split during the 24-hour period, cutting the desired patch piece in half to give two pieces, applying both pieces overnight then removing one in the morning. The stability at 21 and 35°C and uniformity of estradiol distribution has recently been demonstrated for Evorel, Estraderm and Oesclim (50µg, 50µg and 25µg per 24 hours) patches when cut into 8 pieces [24]. Therefore, while a new 25µg patch is normally required each day for older girls, those with a low body weight may receive a second piece during the next 24 hours.

Table 3a Three-year protocol for transdermal 17β - estradiol pubertal induction regimen and a suggested first post-induction year. The dose at the beginning of each year is calculated according to body weight.

	Weight (kg)	50 µg patch	25 µg patch	Duration of treatment, Instructions
Year 1*				
	< 40 kg	1/16 of patch (3.1 µg)	1/8 of patch (3.1 μg)	10-12 hours (overnight, to mimic the normal diurnal variation)
	40-55	1/12 of patch (4.2 μg)	1/6 of patch (4.2 μg)	
	>55	1/8 of patch (6.2 µg)	¼ patch (6.2 μg)	
Year 2				
	< 40 kg	1/8 of patch (6.2 µg)	1/4 of patch (6.2 μg)	10-12 hours (overnight)
	40-55	1/6 of patch (8.3 µg)	1/3 patch (8.3 μg)	
	>55	¼ of patch (12.5 µg)	½ patch (12.5 μg)	
Year 3				
	< 50 kg	1/3 of patch (16.7 μg)	2/3 of patch (16.7 μg)	Cut the desired dose into two halves; attach both parts to the skin in the evening.
	50-65	3/8 patch (18.8 μg)	3/4 patch (18.8 μg)	After 10-12 hours (overnight) remove one part, keep the second part during the day. Remove
	>65	1/2 of patch (25 µg)	1 patch (25 µg)	second part in the evening, before evening application of a two further half patches. This results in a diurnal dose variation, with higher dose nighttime.
Year 4**	Post-induction dose			

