4.6 Data analysis

When the target number of patients has been enrolled (see below), and a sufficient number (84 in each arm) have completed the full 3-year induction, the following analyses between the transdermal and oral groups will be conducted:

- Demographics of patients choosing oral or transdermal estradiol preparations, differences at baseline
- Numbers of patients in each treatment arm, their centres and countries
- Adherence to each of the treatment arms including % of dropouts
- Propensity score matching to reduce bias due to confounding factors e.g. 45,X karyotype, midparental height, height at the beginning of pubertal induction, duration of prior GH treatment, GH responsiveness and treatment or not with oxandrolone.
- Use of Directed Acyclic Graphs to establish the minimally sufficient set of confounders for each outcome parameter, entering these into multivariable regression models

The minority of girls undergoing a 2-year induction will be analysed separately and their outcomes compared with the majority of girls undergoing the full three-year induction

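### The adherence outcome averages capped good/reasonable/poor labels instead of the missed-dose counts behind them, so a girl with one long lapse can rate better than a girl who missed fewer doses

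*Protocol*

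**What the plan says.** Protocol section 3.2, Table 1, lists adherence among the secondary outcomes and defines it as "Average of good, reasonable and poor rating with adherence during pubertal induction (3 years ± X months"). The ratings come from Table 4 in section 4.5: "Scored according to estrogen doses missed per month as good (≤ 2) moderate (≤ 4) and poor (> 4"). The text below Table 4 gives the source, namely that adherence at each visit is "scored according to the number of estrogen doses estimated by the family to have been missed per month". A footnote to the same table sets the visit schedule: "4-monthly visits are recommended; however 3-6 monthly may be more suitable for some participating centres".

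Section 4.6 then plans a comparison by arm: "Adherence to each of the treatment arms including % of dropouts". No section defines an adherence outcome on the counts, and no numeric score is attached to the labels. The middle label is 'reasonable' in Table 1 and 'moderate' in Table 4, and the X in Table 1's period has not been filled in.

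**The concern.** The plan starts from a count, reduces it to three labels and averages the labels. The reduction loses most at the bottom of the scale. Dosing is daily: the oral dose is "given before sleep each night", and for the transdermal route "an overnight patch is applied for 10-12 hours during the first two years of induction". A month can therefore hold about 30 missed doses, yet everything from 5 upwards scores the same.

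An average of such labels measures how many visits were rated poor rather than how much treatment was missed. Two girls can be placed in the wrong order if one misses many doses in a single block and the other misses a few all the time. Acceptability is part of the research question in section 3, and section 6.1.2 says that problems with adherence will be considered in the analysis. The measure should therefore follow the amount missed as closely as the collected data allow.

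**Working it through.** The protocol gives no computed adherence figure, so there is none to reproduce.

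**Inputs**
- Cut-offs (Table 4): good ≤2, moderate ≤4, poor >4 missed doses per month.
- Visits (Table 4 footnote): 4-monthly over a 36-month induction, so 36/4 = 9 ratings. Section 3.2 gives the length: "Induction period is normally 3 years (plus 6 months for very short girls), exceptionally 2 years for girls presenting late".
- Possible doses: one a day, 365/12 = 30.4 per month.
- Scores (assumed, as none is stated): good = 3, moderate = 2, poor = 1.

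**Two girls under the Table 1 rule**

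| | Girl A: 0 in Years 1-2, 30/month in Year 3 | Girl B: 5/month throughout |
|---|---|---|
| Ratings | 6 good, 3 poor | 9 poor |
| Average label | (6×3 + 3×1)/9 = 2.33 | (9×1)/9 = 1.00 |
| Missed per month | (6×0 + 3×30)/9 = 10 | 5 |
| Share of doses taken | 1 − 10/30.4 = 67% | 1 − 5/30.4 = 84% |

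Girl A missed twice as many doses and rates better.

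**How far this depends on the scores.** Girl B is poor at every visit and so has the lowest average possible. Any scoring in which good exceeds poor ranks A above B. The same holds for a girl who misses one dose a week, because 52/12 = 4.33 exceeds 4. If her family reports 4 a month, she is moderate throughout. A then rates better only if the middle score is below 2.33 on the 1-to-3 scale; equal spacing puts it at 2.

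**Other induction lengths, with 12 months missed entirely and the rest rated good.** Over 3.5 years the average is (30×3 + 12×1)/42 = 2.43, still above 2.00. Over 2 years it is (12×3 + 12×1)/24 = 2.00, a tie with a girl who is always moderate and better than one who is always poor.

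**Effect on an arm comparison.** This was simulated under assumptions that are not in the protocol: nine visits, whole-number counts capped at 30, gamma variation between and within girls with shapes 0.5, 1 and 2 in all nine pairings, and the same shapes in both arms. With 84 girls per arm and means of 2 against 3.2 missed doses a month, a t-test on the label average has about 1 to 7 percentage points less power than a t-test on the mean count. At means of 2, 3 and 5, the Spearman correlation between the two measures is 0.91 to 0.98 in size.

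**When it turns into bias.** Suppose girls in both arms miss 10 doses a month on average. If missing is steady in one arm, every rating is poor and the average is 1.00. If it follows Girl A's pattern in the other arm, the average is 2.33. The label average then differs by 1.33 although the amount missed is equal. This is a deliberately extreme case that shows the mechanism; it is not a forecast.

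**The case against.** The strongest reply is that the reversal is an edge case. It needs a lapse packed into one block, good ratings otherwise, and a girl who keeps attending and is not counted as a drop-out. Under ordinary patterns the label average follows the count closely, and its planned use is a comparison between arms, where little power is lost. Families recall over 3 to 6 months, so coarse categories are defensible, and a mean of rough counts gives weight to a few large guesses. Numeric scores and weights are commonly left to the SAP. All of this limits the size of the point. It does not remove it, because the protocol fixes the averaging of labels as the outcome definition, and the labels rest on the same recalled numbers.

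A reader might infer more than the protocol supports in four ways:
- *That the measure favours one route.* This would require missed doses to cluster differently by route, and no section says that they do.
- *That a known share of girls would be misclassified.* The protocol never rounds a girl's average back to a label and never applies the cut-offs to her mean count, so such a percentage would depend on an invented step and on chosen distributions.
- *That drop-outs are hidden.* Percentage drop-outs is a separate item in Table 1, and section 4.6 reports it with adherence.
- *That unequal visit spacing already distorts the average.* The footnote lets spacing differ between centres; it does not say that one girl's intervals vary, and equal weights do no harm where they do not.

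**Conclusion.** The point holds as a minor one on a secondary outcome. As defined in Table 1, the average cannot separate 5 from 30 missed doses a month, and it can rank a girl with one long lapse above a girl who missed half as many doses (2.33 against 1.00, at 10 against 5 a month). That reversal rests on nine equally weighted visits and on any scoring in which good exceeds poor; the figures 2.33 and 1.00 rest on the assumed 3/2/1 scores.

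For the arm comparison the expected cost is small, about 1 to 7 points of power under the assumed gamma patterns, provided that missing follows the same pattern in both arms. A bias is possible but not shown. The primary outcome and the sample size are unaffected.

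**What to change.** In Table 1, replace the averaged rating with missed doses per month over the induction period, or the percentage of scheduled doses missed, weighting each visit by the interval it covers. Have centres send the family-estimated number to the central database as well as the label; the protocol does not say which of the two is entered, and a count cannot be recovered later from a label. Keep the ≤2, ≤4 and >4 categories as a descriptive summary, use one name for the middle category in Tables 1 and 4, and fill in or delete the X in the period.

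The cost is a wording change and one numeric field, with no new visit or procedure. The downside is that recalled counts are rough and large values carry weight; showing the categories beside the mean lets a reader see whether a few large reports drive the result.

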3 RESEARCH QUESTION/AIM(S)

Research question: Is transdermal 17β-estradiol induction superior to oral induction in terms of key parameters including pubertal height gain and adult height, cardiac (e.g. blood pressure), uterine and bone health, and in acceptability?

Study hypothesis: Induction of puberty using transdermal 17β -E2 will result in better outcomes for some key parameters.

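### Satisfaction with the route has no scheduled collection point and no score on leaving, so any score will come mainly from girls who stayed about 3 years on their route

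*Protocol*

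**What the plan says.** The research question in Protocol section 3 asks whether transdermal induction is superior for several parameters, ending with "uterine and bone health, and in acceptability". Section 3.2, Table 1 has an outcome group on satisfaction and adherence. It contains "Patient satisfaction with mode of administration (scoring 1-5 where 5=best" and, as a separate item, "Percentage drop-outs from either regimen". The satisfaction item has no time of its own. The table's caption reads "Outcome measures to be analysed at the end of pubertal induction in girls with Turner syndrome".

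Section 4.5 sets out data collection: "Table 4 shows the recommended information to be collected before, during and at the end of pubertal induction". Table 4 has a row for adherence at visits and at each year end. It has no row for satisfaction at any time, under either the essential or the desirable heading. The text after the table begins its list with "At each visit, measurement of height, weight, blood pressure, pubertal stage, adherence" and goes on to adverse events and concurrent treatment; satisfaction is not in that list either.

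Section 4.6 starts the analysis when "a sufficient number (84 in each arm) have completed the full 3-year induction", and its list of analyses includes "Adherence to each of the treatment arms including % of dropouts". Section 7.5 says that the European centre records dropout. It asks for neither a score nor a reason at that point. Section 5 has data sent to the European centre at enrolment and at the end of each induction year.

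**The concern.** Disliking the tablets or patches is an obvious reason to stop or change route. If nobody asks for the score when that happens, the least satisfied girls are the ones most likely to be missing from the comparison. The mean among those who remain is then too high, and more so in the arm that loses more dissatisfied girls.

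This cannot be left to the analysis plan. An analysis plan can decide how to handle scores that exist, but it cannot recover a score that was never taken. The comparison at stake is the only direct measure of how girls rate the route itself.

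**Working it through.** **What is scheduled**

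| Place in the Protocol | Satisfaction with route | Adherence | Drop-out |
|---|---|---|---|
| 3.2, Table 1 | listed, no time of its own | listed, over the induction period | listed as a percentage |
| 4.5, Table 4 | no row | visits and each year end | no row |
| 4.5, per-visit list | absent | every visit | absent |
| 4.6, list of analyses | not named | named | named, as a percentage |
| 7.5 | absent | non-compliance recorded | recorded, no reason or score asked |

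Read literally, the score is either collected nowhere or, if centres take the caption as the time to ask, collected from girls who reach the end of induction.

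**Inputs.** The documents give no figure for satisfaction and no drop-out rate, so there is no plan figure to reproduce. All inputs below are assumptions.

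**Formula.** In an arm where all starters have mean m, a fraction d leaves, and leavers average L:

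completers' mean = (m − d × L) / (1 − d)

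The completers' mean exceeds m whenever L is below m, and the excess grows with d.

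**Check 1: extreme case.** 105 girls start each route; stayers average 4.0 and leavers 1.5; 20 leave one route and 5 the other.
- All starters: (85 × 4.0 + 20 × 1.5) / 105 = 370 / 105 = 3.52, and (100 × 4.0 + 5 × 1.5) / 105 = 407.5 / 105 = 3.88. Difference 0.36.
- Completers: 4.0 and 4.0. Difference 0.

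**Check 2: leaving driven by the score.** Scores are a normal variable with SD 1 and mean 3.2 or 3.8, rounded and clipped to 1–5. The probability of leaving at scores 1 to 5 is 0.6, 0.4, 0.15, 0.05 and 0.02; a second run multiplies these by 1.5.

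| | Worse route | Better route | Difference |
|---|---|---|---|
| All starters, mean | 3.19 | 3.75 | 0.56 |
| Completers, drop-out 18% v 11% | 3.37 | 3.86 | 0.49 |
| Completers, drop-out 27% v 16% | 3.50 | 3.93 | 0.43 |

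On the worse route the share scoring 2 or less falls from 24% of starters to 17% or 11% of completers.

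**Check 3: can the order reverse?** Leavers average 2.0; drop-out is 30% on the worse route and 10% on the better one, whose true mean is 3.5.
- Better route: (3.5 − 0.1 × 2.0) / 0.9 = 3.67.
- Worse route, true mean 3.3: (3.3 − 0.3 × 2.0) / 0.7 = 3.86. The order reverses.
- Worse route, true mean 2.9: (2.9 − 0.3 × 2.0) / 0.7 = 3.29. The order holds.

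**Check 4: when there is no bias.** If leavers score like stayers, the completers' difference equals the true one. If the routes have equal true means, equal drop-out and equal leaver scores, the difference stays 0.

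**The case against.** A reader might infer that the protocol orders the score to be taken only at the end of induction. It does not. The caption speaks of analysis, and it cannot be a measurement time for every row: the same table holds adherence over the induction period and final adult height. Items meant for the end, such as blood pressure and uterine findings, say so themselves. This objection stands. The defect is that no collection time is set, not that a wrong one is.

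A reader might also take the 84-completers sentence in section 4.6 to limit the analysis to completers. It says when analysis starts, and the list that follows includes drop-outs. How existing scores from leavers enter the comparison can properly be left to the analysis plan.

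The strongest point is that loss is not hidden. Percentage drop-outs stands in the same outcome group. In Check 1 it would show 20/105 against 5/105 (19% v 5%; uncorrected chi-square 10.2, p about 0.001). So the difference in acceptability would still be seen. But without a reason or a last score, a reader cannot separate dislike of the route from a family moving away, and cannot correct the satisfaction means.

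Finally, one might conclude that the route losing more girls will look the better one. The checks do not support that as a general claim: the usual result is a smaller difference, the extreme case is a tie, and reversal needs a wide drop-out gap and a small true difference.

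**Conclusion.** The point holds in this form: a listed outcome that serves the research question has no scheduled collection, and nothing captures a score or a reason from girls who leave their route. The bias favours the arm that loses more dissatisfied girls. Under the assumed inputs it takes 0.07 to 0.13 points off a true difference of 0.56, and in the extreme case removes a difference of 0.36.

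These sizes rest wholly on assumed drop-out and scores, and on leavers being less satisfied than stayers. Severity is minor to moderate: this is one secondary item, drop-out is reported beside it, and neither the primary outcome nor the sample size is affected.

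**What to change.** 1. Add the single 1–5 item to Table 4 at the end of each year, sent with the existing yearly return, and at the visit when a girl stops or changes route.
2. Record the reason for leaving at that visit.
3. State in Table 1 that the comparison covers all girls who started each route, using the last score given on that route.
4. Report the completers' end-of-induction score as a descriptive result next to percentage drop-outs.
5. Optionally, as a sensitivity analysis only, rank girls who left for route-related reasons lowest. This counts drop-out a second time, so it should not be the main result.

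The cost is one extra question per return, one question and a reason at leaving, and amended wording in Tables 1 and 4. Leavers' scores will be taken at different durations of treatment, and a girl who disappears before her first yearly return will still have no score.
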